5.6 Specimen Collection

5.6.1 Respiratory Mucosal Samples

Respiratory mucosal specimens will be self-collected and tested according to rapid antigen test FDA and manufacturer guidelines.

During this study, a standard respiratory specimen is defined as a participant-collected anterior nasal swab using a rapid antigen test. Participants will take a digital photo of their test result and upload the file to database platform.

- Participants will be asked to self-collect a respiratory specimen each week regardless of symptoms throughout the study surveillance period. For weekly and illness testing, participants will use FDA-approved COVID-19 Rapid Antigen Self-Test. Ideally, the sample will be collected no later than 24 hours from the weekly text notification or illness onset. Participants will receive detailed written and/or visual instructions for self-collection of a respiratory specimen (Appendix V3 Test Instructions Video Script and Appendix V4 Test and Upload Instructions). At the vaccination visit, participants will be given a "self-collection kit" that includes written and/or visual instructions, and all prepared supplies for routine, weekly specimen collection and for acute illness specimen collection. Study staff will track the use of kits and ship replacements to participants as needed.
- The study will provide all participants with the OSANG Healthcare (OHC) COVID-19 Antigen Self
 Test. The OHC COVID-19 Antigen Self Test is the sole test for the study. The OHC Self Test is
 authorized for non-prescription of home use with self-collected anterior nasal swab samples
 from individuals 14 years or older.³⁷

5.6.2 SARS-CoV-2 Rapid Antigen Test Results

State or local health department regulations may require reporting of incident cases of SARS-CoV-2 infection. The Investigator will be responsible for contacting state or local SARS-CoV-2 surveillance coordinators to ensure study procedures comply with all reporting requirements.

Participants will be informed that:

- Results are not meant to replace recommended clinical and/or occupational molecular tests;
- False positive and false negative results are possible;
- Receiving a negative diagnostic result should not alter their preventive behaviors, given that
 results are specific to the date and time they are collected, and current assays may not be
 sensitive to all infections;
- Results will not be shared with the participants' medical providers.
- Participants should consult their personal medical provider if they have questions, concerns, or any medical needs related to their illness;
- They should follow their employer's guidelines for reporting illnesses and returning to work.

6. Statistical Considerations

This randomized, three arm, active comparator trial will compare the clinical efficacy of NVX 2023-2024 updated vaccine (Arm 1) with a single dose of the mRNA 2023-2024 updated strain (Arm 2) as well as non-boosted comparison group (Arm 3). The study hypotheses are 1) to compare vaccine efficacy (VE) between participants who receive either the NVX (Arm 1) or mRNA 2023-2024 updated strain (Arm 2) with the non-boosted participants who are recommended to be boosted based on CDC, state or organizational guidelines but decline the 2023-2024 updated vaccine and 2) to determine the relative vaccine efficacy (relative VE) of the Pfizer mRNA 2023-2024 updated vaccine and the NVX 2023-2024 updated vaccine in preventing SARS-CoV-2 infection to confirm non-inferiority for NVX. Detailed plans for statistical analysis are provided in Appendix S1. Statistical Analysis Plan (SAP) and Appendix S2. Post-Vaccination SAP. These plans have been updated to reflect revised power calculations based on more accurate estimations of assumed rates of infection throughout the study period. As a result of these revised power calculations, the surveillance period has been expanded from 20 to 24 weeks to ensure sufficient data capture within the study.

6.1 Sample size & Power Considerations

6.1.1 Sample Size for Primary Objectives

Power and sample size are examined for both primary objectives to 1) compare VE between vaccinated arms (both NVX and mRNA) and the non-vaccinated comparison arm with a 2-sided alpha=0.05 superiority test and 2) determine non-inferiority of NVX 2023-2024 formula vaccine variant compared to a single dose of Pfizer mRNA 2023-2024 updated vaccine with a 1-sided alpha=0.05 confidence interval. The rate of CLI-associated SARS-CoV-2 infection, confirmed by COVID-19 rapid antigen test (RAT) in those not vaccinated with the 2023-2024 formulation is expected to be 60 per 100,000 person-days. We expect those choosing not to vaccinate in Fall 2023 to Spring 2024 to be a mix of unvaccinated and fully vaccinated but not boosted individuals, but to be conservative we will assume this group is solely comprised of fully vaccinated individuals. Using publicly available data on the historic case rates in Utah for COVID-19 from the week of November 20, 2022 to the week of July 30, 2023, 39 the average rate of cases in those fully vaccinated in Fall 2022-Spring 2023 is 39.64 per 100,000 person-days for those fully

vaccinated. From a survey conducted in spring of 2022, it has previously been reported that of those testing for COVID-19 44.2% report testing at a lab or clinic and 25.7% reported testing at a drive-thru clinic⁴⁰. Therefore, using at-home test kits to identify cases, we expect rates to be 43.1% higher (1/(0.257+0.442)) than what is shown on Utah's dashboard. This under-reporting adjustment to Utah's observed rates from last fall leads to a conservative estimate for the rate of CLI-associated SARS-CoV-2 infection, confirmed by COVID-19 rapid antigen test (RAT), in those not vaccinated with the 2023-2024 formulation to be 60 per 100,000 person-days. Using the same logic applied to the reports for those with a bivalent booster last fall, after adjusting for under-reporting, we estimate the infection rate to be 48 per 100,000 person-days in those vaccinated in Fall 2023 to Spring 2024.

For the superiority test of the first primary objective, on which the sample size is based, the null hypothesis that vaccine efficacy, or VE, of the 2023-2024 formula compared to no vaccination in Fall 2023-Spring 2024 is 0 is tested against the alternative that the VE is not equal to 0. That is, H_0 : VE = 0 is tested against H_a: VE ≠ 0. VE is calculated as 1- hazard ratio, HR, comparing those receiving the 2023-2024 formulation (either NVX or Pfizer) to those choosing not to be vaccinated in Fall 23 to Spring 24, times 100 or 100*(1-HR). HR will be estimated using Cox proportional hazards models with α =0.05. Table 4 provides the required sample size to yield 80% power to detect VE of 40%, 50%, and 60% or higher, assuming an attrition rate of 15% or less. We plan that the NVX and Pfizer arms will each have twice as many participants as the arm of those choosing no Fall 2023 to Spring 2024 vaccination, a ratio of 4:1. Calculations were made in PASS using the Multi-Arm Tests for Treatment and Control Survival Curves using Cox's Proportional Hazards Model⁴¹. In 24 weeks of follow-up, the rate of 60 cases per 100,000 person-days equates to an event probability of 10.08%. This probability corresponds to a hazard rate of 0.10625. With a total of 1500 participants enrolled (1200 with 2023-2024 formulation and 300 without Fall 2023 to Spring 2024 vaccination), we have 80% power to detect a VE of 56.25% or more, even if we see 15% attrition. With 1500 enrolled and an observed VE of 50%, we anticipate there will be approximately 85 RAT confirmed symptomatic COVID-19 cases in total (30 in the not vaccinated arm and 55 in the vaccinated arm) with no attrition, and 72 with 15% attrition.

Table 4. Relationship between Vaccine Efficacy and Sample Size, assuming a 4:1 ratio vaccinated						
with 2023-2024 formulation to not vaccinated in Fall 2023-Spring 2024 and 15% rate of attrition.						
Lowest Detectable VE comparing between non-vaccinated and Sample size for 80% power						
vaccinated (NVX and Pfizer combined) arms						
40%	3,183					
50%	1,954					
56.25%	1,500					
60%	1,289					

For the non-inferiority test in the second primary objective, the null hypothesis that the NVX vaccine of 2023-2024 formulation is inferior to the Pfizer vaccine of the 2023-2024 formulation is tested against the alternative that NVX is non-inferior. That is, H_0 : $rVE < 0 + \delta$ is tested against H_a : $rVE \ge 0 + \delta$, where δ is the "interval of equivalence", the range in which the effectiveness of the two vaccines would be considered clinically equivalent. Relative VE, or rVE, is calculated as 1- hazard ratio, HR, comparing

those receiving the NVX 2023-2024 formulation to those receiving the Pfizer 2023-2024 formulation, times 100, or 100*(1-HR). We believe an interval of -50% would be clinically acceptable. For example, if Pfizer reduces the hazard of infection by half, reducing the hazard by 25% (VE of 25%) would correspond to an rVE of -50%. Similarly, if Pfizer shows 80% VE compared to the non-vaccinated, a NVX VE of 70% would correspond to an rVE of -50%. For the power calculations for the second primary objective, the significance level is α =0.05.

Table 5 gives the power for testing the non-inferiority hypothesis with a sample of 600 enrolled patients per arm with an equivalence interval of -50%, with observed rVE ranging from -20 to 20 and observed rates of CLI-associated SARS-CoV-2 infection, confirmed by COVID-19 rapid antigen test (RAT) in the Pfizer arm ranging from 50 to 90 per 100,000 person-days. Additionally, an attrition rate of 15% from 600 is assumed. The power decreases as the observed case-rate in the Pfizer arm decreases or as the observed rVE decreases. Calculations were made in PASS 2023 using Non-Inferiority Tests for Vaccine Efficacy using the Hazard Ratio (Cox's Proportional Hazards Model). If we assume an infection rate of 60 per 100,000 person-days in the Pfizer vaccinated arm we have 81.12% power to determine non-inferiority of NVX for observed rVEs of 10 or greater.

Table 5. Power assuming 600 at enrollment for each group (NVX and Pfizer) accounting for 15% attrition for non-inferiority of NVX vs. Pfizer 2023-2024 formulations and a non-inferiority limit of -50 rVE.

Assumed rate of COVID-19 infection in 100,000 person days for Pfizer 2023-2024			Possible C	bserved Re	elative VE		
formulation arm	20	10	5	0	-5	-10	-20
50	86.88	74.60	67.13	59.16	51.02	43.03	28.63
60	91.71	81.12	74.00	65.94	57.33	48.57	32.20
70	94.84	86.12	79.58	71.75	62.97	53.70	35.66
80	96.84	89.88	84.08	76.70	67.98	58.41	38.98
90	98.08	92.68	87.66	80.86	72.41	62.72	42.16

With a planned sample size of 600 per arm and 15% attrition, if the observed rate of infection in the Pfizer 2023-2024 formulation arm differs from 60 per 100,000 person-days, 600 participants in each arm assures 80% power to claim non-inferiority for observed rVE greater than 10, sometimes less than 10, as outlined in the table above. The grey cells in the table indicate which scenarios will have 80% power with 600 participants.

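### The protocol's stated inputs give a comparison-group rate of 56.7 per 100,000 person-days, not the 60 it plans on; at 56.7 the stated 80% power is about 78%

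*Protocol*

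**What the plan says.** Protocol section 6.1.1 builds the comparison-group rate in two steps. It reports that "the average rate of cases in those fully vaccinated in Fall 2022-Spring 2023 is 39.64 per 100,000 person-days", and then, because the trial uses home tests, "we expect rates to be 43.1% higher (1/(0.257+0.442)) than what is shown on Utah's dashboard". From these it concludes that the rate "in those not vaccinated with the 2023-2024 formulation is expected to be 60 per 100,000 person-days", and it describes the adjustment as one that "leads to a conservative estimate for the rate of CLI-associated SARS-CoV-2 infection". The word appears once before, on a different matter: "to be conservative we will assume this group is solely comprised of fully vaccinated individuals".

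The rate of 60 is then converted to a 24-week event probability of 10.08% and a hazard of 0.10625. With 1,200 vaccinated and 300 not vaccinated, the section states that "we have 80% power to detect a VE of 56.25% or more, even if we see 15% attrition". Table 4 gives sample sizes for 80% power of 3,183, 1,954, 1,500 and 1,289 at VE of 40, 50, 56.25 and 60%. The section also expects about 85 cases (30 and 55) without attrition and 72 with 15% attrition, and attributes both figures to an observed VE of 50%.

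SAP section 4.1 applies the same factor to a different historic rate, 56.63, and plans on 80.

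**The concern.** The two stated inputs do not multiply to the stated rate, and nothing in the text accounts for the difference. The direction matters. Power for a Cox comparison depends on the number of events, so planning on a rate above what the inputs support overstates power. Calling the result conservative tells a reader that there is margin where the inputs provide none.

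The protocol says that the sample size rests on this first primary objective, and VE 56.25% is the effect at which Table 4 requires exactly 1,500 participants. The headline claim therefore has no slack to absorb a lower rate.

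**Working it through.** **Inputs** (protocol 6.1.1): historic rate 39.64 per 100,000 person-days; testing shares 0.257 and 0.442; follow-up of 24 weeks, or 168 days; 1,200 and 300 enrolled; 15% attrition, leaving 1,020 and 255; two-sided alpha 0.05; VE 56.25%, so HR = 0.4375.

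**Step 1, the rate.** 1/(0.257 + 0.442) = 1/0.699 = 1.4306. Then 39.64 × 1.4306 = 56.71. Reaching 60 would need a historic rate of 60 × 0.699 = 41.94. The planning rate is 60/56.71 − 1 = 5.8% above the product of its inputs. For the SAP, 56.63/0.699 = 81.0 against a planned 80, so there the rounding is downward.

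**Step 2, reproduce the plan's figures at 60.**
- Comparison-group event probability: p0 = 60 × 168/100,000 = 0.1008. Hazard over follow-up: h = −ln(1 − 0.1008) = 0.10625. Both match the protocol.
- Vaccinated event probability: p1 = 1 − exp(−0.10625 × 0.4375) = 0.0454.
- Events: 255 × 0.1008 + 1,020 × 0.0454 = 25.7 + 46.3 = 72.0.
- Schoenfeld power: Φ(√(D × 0.2 × 0.8) × |ln HR| − 1.96) = Φ(√(72.0 × 0.16) × 0.8267 − 1.96) = Φ(0.85) = 80.1%.
- Setting power to 80% and solving for N gives 3,179 / 1,952 / 1,495 / 1,286, against 3,183 / 1,954 / 1,500 / 1,289 in Table 4. All are within 0.4%. The same formula at a rate of 80 gives 2,372 / 1,455 / 958, against the SAP's 2,378 / 1,460 / 960.

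**Step 3, the same formula at 56.7.**
- p0 = 0.0953, h = 0.1001, p1 = 0.0429.
- Events at VE 56.25% after attrition: 24.3 + 43.7 = 68.0.
- Power: Φ(√(68.0 × 0.16) × 0.8267 − 1.96) = Φ(0.77) = 77.8%.

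| Quantity | Rate 60, recomputed | Rate 56.7 |
|---|---|---|
| Power at VE 56.25%, N = 1,500 | 80.1% | 77.8% |
| Detectable VE at 80% power, N = 1,500 | 56.2% | 57.6% |
| N for VE 40% | 3,179 | 3,367 |
| N for VE 50% | 1,952 | 2,067 |
| N for VE 56.25% | 1,495 | 1,583 |
| N for VE 60% | 1,286 | 1,362 |

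**Sensitivity to convention at 56.7.** Taking the vaccinated risk as p0 × HR gives 77.1% power. Treating the rate as a hazard throughout gives 75.9%. At 60 these two conventions give 79.4% and 78.1%, and they fit Table 4 less well.

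**Step 4, the case counts.** At a rate of 60 without attrition, VE 56.25% gives 30.2 + 54.5 = 84.7 cases, and 72.0 after 15% attrition. These are the printed 85 and 72. VE 50% gives 30.2 + 62.1 = 92.3, and 78.5 after attrition. At 56.7, VE 50% gives 74.1 after attrition.

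**The case against.** The 80% is correctly calculated from its stated premise: 60 leads to 10.08%, 0.10625 and 80%. The 78% appears only once that premise is replaced by the product of the inputs. That is right. The fault lies in how the rate was reached, not in the power calculation.

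The gap is also small beside the uncertainty of the input. The SAP uses a different historic window and its rate of 56.63 is 43% above 39.64. This bears on how much weight the point carries, but not on whether the stated inputs should yield the stated rate.

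The word conservative might refer to something other than rounding. One candidate is the assumption that the comparison group is entirely fully vaccinated. That assumption is already contained in the 39.64, and it adds little because protocol section 5.3 requires at least two mRNA doses. Another candidate is that weekly testing of everyone, with or without symptoms, could find more cases than the adjusted dashboard rate. The documents do not settle that. Neither reading explains how 56.7 becomes 60.

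A reader might go further in two ways that the documents do not support.
- One could divide 48, the rate given for vaccinated people, by 56.7 and say that the implied VE is 15% rather than 20%. The raw rate behind 48 is not given. If 48 had been raised in the same proportion, from about 45.4 (48 × 56.7/60), the ratio would still imply 20%. The power claim does not use 48.
- One could say that the expected 72 cases are overstated. The protocol attaches 72 to VE 50%, and at that VE even a rate of 56.7 gives about 74. The fault in that sentence is the label.

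**Conclusion.** The point stands as a small correction. The stated inputs give 56.7, the protocol plans on 60 without a described step, and the difference favours power. With the formula that reproduces Table 4, power at VE 56.25% is about 78% rather than 80%, a loss of about 2.3 points and 4 events. Equivalently, 1,500 participants detect a VE of about 57.6% at 80% power.

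This rests on 39.64 and the two testing shares being the only inputs, on 15% attrition removing participants entirely, and on the event-probability convention that best fits Table 4. It does not show that the trial is inadequately sized or that enrolment must rise. It shows that the headline figure and its label do not follow from the inputs given.

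**What to change.** In protocol section 6.1.1, do one of two things:
- Use 56.7 in the text. Revise Table 4 to about 3,367 / 2,067 / 1,583 / 1,362 for VE 40 / 50 / 56.25 / 60%. State either a detectable VE of about 57.6% with 1,500 enrolled or power of about 78% at VE 56.25%. The sponsor should rerun its own software for the final digits.
- Keep 60 and state its basis, whether an unrounded input or a further adjustment.

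In either case, do not describe the move from 56.7 to 60 as conservative. If the word is meant for the composition of the comparison group or for the testing schedule, say so there.

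In the same edit, correct the case counts. At a rate of 60, either relabel 85 and 72 as VE 56.25%, or keep VE 50% and print about 92 (30 and 62) and 78. If 56.7 is adopted, the figures after attrition are 68 at VE 56.25% and 74 at VE 50%.

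The cost is a few restated figures, slightly less favourable. Enrolment, procedures and analysis are unchanged.

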For the superiority test of the first primary objective, on which the sample size is based, the null hypothesis that vaccine efficacy, or VE, of the 2023-2024 formula compared to no vaccination in Fall 2023-Spring 2024 is 0 is tested against the alternative that the VE is not equal to 0. That is,  $H_0$ : VE = 0 is tested against  $H_a$ : VE  $\neq 0$ . VE is calculated as 1- hazard ratio, HR, comparing those receiving the 2023-2024 formulation (either NVX or Pfizer) to those choosing not to be vaccinated in Fall 23 to Spring 24, times 100 or 100\*(1-HR). HR will be estimated using Cox proportional hazards models with  $\alpha$ =0.05. Table 1 provides the required sample size to yield 80% power to detect VE of 40%, 50%, and 60% or higher, assuming an attrition rate of 15% or less. We plan that the NVX and Pfizer arms will each have twice as many participants as the arm of those choosing no Fall 2023 to Spring 2024 vaccination, a ratio of 4:1. Calculations were made in PASS using the Multi-Arm Tests for Treatment and Control Survival Curves using Cox's Proportional Hazards Model. In 24 weeks of follow-up, the rate of 80 cases per 100,000 person-days equates to an event probability of 13.44%. This probability corresponds to a hazard rate of 0.14433. With a total of 1500 participants enrolled (1200 with 2023-2024 formulation and 300 without Fall 2023 to Spring 2024 vaccination), we have 80% power to detect a VE of 50% or more, even if we see 15% attrition. With 1500 enrolled and an observed VE of 50%, we anticipate there will be approximately 124 RAT confirmed symptomatic COVID-19 cases in total (41 in the not

vaccinated arm and 84 in the vaccinated arm) with no attrition, and 106 with 15% attrition.

Table 1. Relationship between Vaccine Efficacy and Sample Size, assuming a 4:1 ratio vaccinated with 2023-2024 formulation to not vaccinated in Fall 2023-Spring 2024 and 15% rate of attrition.

Lowest Detectable VE comparing between non-vaccinated	Sample size for 80% power			
and vaccinated (NVX and Pfizer combined) arms				
40%	2,378			
50%	1,460			
60%	960			

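### Rate × 168 days is labelled an event probability and converted to a hazard a second time, which inflates planned events by about 5% (protocol) and 7% (SAP) and overstates headline power by about 2 to 2.7 points

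*Protocol*

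**What the plan says.** Protocol Section 6.1.1 sets the infection rate "in those not vaccinated with the 2023-2024 formulation is expected to be 60 per 100,000 person-days". It then says: "In 24 weeks of follow-up, the rate of 60 cases per 100,000 person-days equates to an event probability of 10.08" percent, followed by "This probability corresponds to a hazard rate of 0.10625". From this it concludes, for 1,200 vaccinated and 300 unvaccinated participants, that "we have 80% power to detect a VE of 56.25% or more, even if we see 15% attrition". Table 4 gives sample sizes for 80% power at four VE values. For non-inferiority, at 60 per 100,000 person-days in the Pfizer arm, the section reports that "we have 81.12% power to determine non-inferiority of NVX for observed rVEs of 10 or greater". Table 5 gives power over a grid of rates and rVE values.

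SAP Section 4.1 follows the same path from a rate of 80 per 100,000 person-days, which "equates to an event probability of 13.44%. This probability corresponds to a hazard rate of 0.14433". It claims 80% power at VE 50% with 1,500 enrolled. SAP Table 1 is the counterpart of protocol Table 4. SAP Table 2 has the same cells as protocol Table 5.

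**The concern.** A rate expressed per person-day is a hazard. Multiplied by the length of follow-up it gives a cumulative hazard, and the probability follows as 1 − exp(−hazard). The plan calls the product a probability and then applies −ln(1 − p) to it. That transformation is right for a probability, but here it acts on a quantity that is already a hazard. The result is a larger hazard, and so more events, than the stated rate implies.

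The design's headline claims sit close to their 80% target, so a small inflation of events can carry them across it. Protocol Section 6 also says that the power calculations were revised to reflect more accurate infection rates and that surveillance was lengthened from 20 to 24 weeks as a result. The rate input is therefore one the plan relies on.

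**Working it through.** **Inputs.** From protocol Section 6.1.1:
- rate 60 per 100,000 person-days; 24 weeks = 168 days
- 4:1 allocation, so the comparison arm's share is 0.2
- 15% attrition
- superiority tested "with a 2-sided alpha=0.05 superiority test"
- non-inferiority tested "with a 1-sided alpha=0.05 confidence interval", margin rVE −50 (HR 1.5), 600 per arm, 510 after attrition

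From SAP Section 4.1: rate 80, otherwise the same design.

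**Conversion.**
- Protocol: 60/100,000 × 168 = 0.1008. The plan takes −ln(1 − 0.1008) = 0.10625, and 0.10625/168 × 100,000 = 63.2 per 100,000 person-days. A single conversion keeps the hazard at 0.1008, with probability 1 − exp(−0.1008) = 9.59%.
- SAP: 80/100,000 × 168 = 0.1344. The plan takes −ln(1 − 0.1344) = 0.14433, which is a rate of 85.9. A single conversion gives hazard 0.1344 and probability 12.58%.

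**Formulas.**
- Events for enrolled N: D = 0.85N × [0.2(1 − exp(−h)) + 0.8(1 − exp(−h·HR))].
- Superiority (Schoenfeld): power = Φ(√(0.16·D)·|ln HR| − 1.96).
- Non-inferiority: D = 510 × [(1 − exp(−h)) + (1 − exp(−h·HR))]; power = Φ(√(D/4)·(ln 1.5 − ln HR) − 1.645).

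**Reproducing the plan with its twice-converted hazard, then using the single conversion:**

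| Row | Printed N | N, plan's hazard | N, single conversion | Power at printed N, single conversion |
|---|---|---|---|---|
| Protocol VE 40% | 3,183 | 3,179 | 3,345 | 78.0% |
| Protocol VE 50% | 1,954 | 1,952 | 2,053 | 78.0% |
| Protocol VE 56.25% | 1,500 | 1,495 | 1,573 | 78.1% |
| Protocol VE 60% | 1,289 | 1,286 | 1,353 | 78.1% |
| SAP VE 40% | 2,378 | 2,372 | 2,538 | 77.4% |
| SAP VE 50% | 1,460 | 1,455 | 1,557 | 77.4% |
| SAP VE 60% | 960 | 958 | 1,026 | 77.4% |

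The plan's hazard reproduces every printed N to within 6. The single conversion does not, so the second conversion is what was entered in the software and is not merely loose wording.

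**Headline at N = 1,500.**
- Protocol, VE 56.25%: 72.0 events and 80.1% power on the plan's hazard; 68.5 events and 78.1% on the single conversion. Event ratio 72.0/68.5 = 1.05. Power of 80% needs VE of about 57.4%.
- SAP, VE 50%: 105.3 events and 81.2% power become 98.4 events and 78.5%. Event ratio 105.3/98.4 = 1.07.

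**Non-inferiority, rate 60, rVE 10 (HR 0.9).** ln(1.5/0.9) = 0.5108.
- Plan's hazard: D = 97.9, so Φ(0.5108 × √24.48 − 1.645) = 81.1% (printed 81.12%).
- Single conversion: D = 93.1, so Φ(0.5108 × √23.28 − 1.645) = 79.4%.

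All 35 cells of Table 5 reproduce within 0.02 points with the plan's conversion. With the single conversion they fall by 0.7 to 2.8 points. Twelve printed cells are at or above 80%. Two of them drop below: rate 60/rVE 10 (81.12 to 79.4) and rate 90/rVE 0 (80.86 to 78.25). The other ten stay above, for example 91.71 to 90.5 and 84.08 to 81.9.

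**Printed case counts.** The protocol gives 85 cases (30 + 55), or 72 with attrition, and labels them VE 50%. On the plan's hazard, VE 56.25% gives 30.2 + 54.5 = 84.7 (72.0 with attrition), while VE 50% gives 30.2 + 62.1 = 92.3 (78.5). The printed counts are therefore the VE 56.25% counts. With a single conversion they become 28.8 + 51.8 = 80.5 (68.5) at VE 56.25%, and 28.8 + 59.0 = 87.7 (74.6) at VE 50%.

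**The case against.** Four arguments can be made for leaving the figures alone.

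- **Attrition.** The fall below 80% assumes that the 15% contribute no follow-up at all. The planned analysis censors participants at their last surveillance response (protocol Section 6.1.2, SAP Section 7.2), so dropouts would contribute time. If the 15% were lost at a constant rate over 24 weeks (an assumption), power with the single conversion would be 81.4% at VE 56.25%, 81.8% for the SAP at VE 50%, and 82.3% for non-inferiority at rate 60 and rVE 10. This stands as a reason to state the attrition assumption. It does not rescue the printed figures, which reproduce only with 15% removed outright.
- **The rate may be a risk.** If the Utah dashboard reports cases over a fixed population, summing over 168 days gives a cumulative proportion, and −ln(1 − p) would be the correct single conversion. The documents do not give the dashboard's denominator. They do express the rate in person-days throughout, and the point follows that text.
- **Precision.** The 60 is itself rounded up: 39.64 × 1.431 = 56.7. At 56.7 with the single conversion, power at VE 56.25% is 75.9%. The input is therefore uncertain by about as much as the error, and Table 5 already varies the rate from 50 to 90. This limits the importance of the point but does not make the conversion right.
- **Overreach.** A reader might infer that every power figure printed at 80% or more falls below 80%, or that the printed 85 and 72 cases are 5% too many. Neither is supported. Ten of the twelve such Table 5 cells stay at or above 80%. At their printed label of VE 50%, the counts of 85 and 72 are slightly too low (87.7 and 74.6), because the label is wrong. The 5% excess holds only at equal VE.

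**Conclusion.** The point holds. Both documents apply the probability-to-hazard conversion to a quantity that is already a hazard, and the printed tables carry the result. On the plan's own inputs and method, every row of protocol Table 4 has 78.0–78.1% power and every row of SAP Table 1 about 77.4%, against the 80% stated. Of the headline claims, 1,500 participants at VE 56.25% loses about 2 points, the SAP's 1,500 at VE 50% about 2.7, and the non-inferiority figure about 1.7.

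This rests on reading the rate as cases per person-day at risk, as the text words it, and on removing 15% of participants outright, as the printed figures require. The shortfall is a misstatement of power. A reader might take it to mean that the trial must enrol more participants, but a difference of this size does not threaten the design.

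**What to change.** 1. Reconcile the comparison-arm rate first: the protocol uses 60 and the SAP 80 per 100,000 person-days. Recomputing the SAP at 80 before that is settled would be wasted work.
2. Enter hazard = rate × 168/100,000 (0.1008 at 60; 0.1344 at 80) and report the event probability as 1 − exp(−hazard), i.e. 9.59% or 12.58%.
3. Re-run protocol Tables 4 and 5 and SAP Tables 1 and 2, and restate the power sentences. At rate 60 these become about 78% power at VE 56.25% (or 80% at VE of about 57.4%) and 79.4% for non-inferiority at rVE 10.
4. State how the 15% attrition enters the calculation. If the dashboard figure is meant as a cumulative proportion, say so and give its denominator.
5. Recompute the expected case counts at a correctly labelled VE: at rate 60, about 80.5 (68.5 with attrition) at VE 56.25%, or 87.7 (74.6) at VE 50%.

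The cost is a re-run of the same software and edits to two tables and a few sentences in each document. Stated power becomes slightly less favourable. No additional participants are needed.

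### The stated 80% power for vaccine versus no vaccine comes from an approximation that is conservative at 4:1 allocation and HR 0.44: on the same inputs an unadjusted Cox test has about 89% power, and the planned covariate adjustment takes back part or all of the difference

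*Protocol*

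**What the plan says.** Protocol section 6.1.1 sizes the trial on the comparison of both vaccine arms combined with the group that declined vaccination, "with a 2-sided alpha=0.05 superiority test". It says that "HR will be estimated using Cox proportional hazards models", and that VE is 100 × (1 − HR). The inputs are a 4:1 allocation, attrition of 15%, and an unvaccinated event probability that follows from the daily rate: "In 24 weeks of follow-up, the rate of 60 cases per 100,000 person-days equates to an event probability of 10.08"%, converted to a hazard of 0.10625. "With a total of 1500 participants enrolled (1200 with 2023-2024 formulation and 300 without Fall 2023 to Spring 2024 vaccination"), the Protocol concludes that "we have 80% power to detect a VE of 56.25% or more, even if we see 15% attrition". Table 4 asks for 3,183, 1,954, 1,500 and 1,289 participants for VE of 40%, 50%, 56.25% and 60%.

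SAP section 4.1 uses the same structure with 80 instead of 60 cases per 100,000 person-days (event probability 13.44%, hazard 0.14433). It concludes that "we have 80% power to detect a VE of 50% or more, even if we see 15% attrition", and its Table 1 asks for 2,378, 1,460 and 960 for VE of 40%, 50% and 60%.

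Both documents name a PASS multi-arm Cox procedure. Neither writes out the formula, gives a simulation check, or makes an allowance for covariates. The analysis sections (Protocol 6.1.2, SAP 7.1 and 8.3.1) plan a Cox model adjusted for age, prior COVID-19 vaccination and week.

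**The concern.** The usual closed-form power formula for a Cox model takes the information as events × (share vaccinated) × (share unvaccinated). That is accurate when the HR is near 1, because events then fall in proportion to group size. Here 80% of participants are vaccinated and the HR behind the headline is 0.4375, so the unvaccinated 20% supply far more than 20% of the events. The Protocol shows this next to Table 4: it expects 30 cases in the unvaccinated arm and 55 in the vaccinated arm, so 35% of cases come from 20% of participants.

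At stake are the lowest detectable VE and the sample sizes in both tables, which tell readers what the trial can show. Protocol section 6 also says that revised power calculations led to surveillance being extended from 20 to 24 weeks, so these figures have already informed a design decision.

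**Working it through.** **Inputs** (Protocol 6.1.1): two-sided α 0.05; target power 80%; 1,500 enrolled; 15% attrition, so 1,275 evaluable (255 unvaccinated, 1,020 vaccinated); 24-week event probability 0.1008 if unvaccinated (60/100,000 × 168 days); cumulative hazard −ln(1 − 0.1008) = 0.10625.

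**Step 1: reproduce the plan's figure.** At HR 0.4375:
- Vaccinated event probability: 1 − exp(−0.10625 × 0.4375) = 0.0454.
- Pooled event probability: 0.2 × 0.1008 + 0.8 × 0.0454 = 0.0565.
- Events required: (1.960 + 0.842)² / (0.8 × 0.2 × (ln 0.4375)²) = 7.849/0.1093 = 71.8.
- Enrolment required: 71.8/0.0565 = 1,271 evaluable, and 1,271/0.85 = 1,495.
- Power at 1,500: 1,275 × 0.0565 = 72.0 events; √(72.0 × 0.16) × 0.827 − 1.960 = 0.85, giving 80.1%.

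The other rows come out at 3,179, 1,952 and 1,286 against the stated 3,183, 1,954 and 1,289. Power at the stated sizes is 80.0–80.1% for all four rows of Table 4 and 80.1% for the three rows of SAP Table 1. One-sided α and the Freedman formula do not reproduce the table.

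**Step 2: check the event split.** Evaluable events at HR 0.4375 are 255 × 0.1008 = 25.7 unvaccinated and 1,020 × 0.0454 = 46.3 vaccinated, a 36/64 split. The formula assumes 20/80.

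**Step 3: power on the same inputs.** Exponential event times, censoring at 24 weeks, 255 v 1,020, unadjusted Cox model, 40,000 replicates:

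| True VE | Events formula | Score | Wald | Likelihood ratio |
|---|---|---|---|---|
| 56.25% | 80.1% | 89.1% | 88.8% | 87.4% |
| 50% | 69.0% | 79.4% | 78.9% | 76.8% |

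Simulated type I error at HR 1 is about 5%, so the extra power does not come from an inflated test. If the 15% leave evenly over follow-up instead of contributing no time, score and Wald power is about 91% and 81–82%.

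**Step 4: closed-form cross-check, two proportions at VE 56.25%.**
- Difference: 0.1008 − 0.0454 = 0.0554.
- Null standard error: √(0.0565 × 0.9435 × (1/255 + 1/1,020)) = 0.01617.
- Alternative standard error: √(0.1008 × 0.8992/255 + 0.0454 × 0.9546/1,020) = 0.01995.
- (0.0554 − 1.96 × 0.01617)/0.01995 = 1.19, giving 88.3%.

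The same calculation gives 78.8% at VE 50%. With the SAP's inputs (0.1344 and 0.0696, VE 50%) it gives 88.2%, in line with simulated 88–89%. A Wald formula using 1/25.7 + 1/46.3 as the variance gives 91.9%, somewhat above the simulation.

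**Step 5: the tables' own sizes.** Simulated score and Wald power is about 87% (VE 40%, 3,183), 87–88% (VE 50%, 1,954) and 89–90% (VE 60%, 1,289). At VE 50%, 80% is reached at about 1,500–1,550 enrolled.

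**Step 6: the planned adjustment.** If the covariates explain a fraction R² of the variance in vaccine group, information falls by about (1 − R²). R² is an assumption; the documents give none.
- From 89% at VE 56.25%: (1.227 + 1.960) × √0.9 − 1.960 = 1.06 (86%) at R² 0.1, and 0.89 (81%) at R² 0.2.
- From 79% at VE 50%: about 75% and 70%.
- Simulating an adjusted Wald test (3,000 trials per cell) gives 85.3% and 80.2% at VE 56.25%, and 73.8% and 68.8% at VE 50%.
- Power at VE 56.25% returns to 80% at R² = 1 − (2.802/3.187)² ≈ 0.23.

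**The case against.** The strongest reply is that nothing has been miscalculated. The tables are correct outputs of a standard approximation in named software, and the approximation errs on the safe side. That stands. A reader might infer an arithmetic slip; the match in every row rules that out.

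The reply continues that 89% is not the power of the planned analysis, because the planned model is adjusted and vaccine choice is likely to be related to age and prior doses. This also stands. At R² near 0.2 the Protocol's 80% at VE 56.25% is about right. It would be right by accident, though: one unstated approximation offsets another unstated cost, and the documents show neither.

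Two stronger readings are tempting. One is that 1,500 could be cut, or that the lowest detectable VE should simply be restated as 50%. The documents do not support this: unadjusted power at VE 50% is just under 80%, and with modest adjustment it is 69–75%, so a conservative headline would become an optimistic one. The other is that the trial is comfortably powered. The Protocol's own expected rates of 48 and 60 per 100,000 person-days imply VE of 1 − 48/60 = 20%, far below either detectable value. That is a separate planning matter, which this correction does not touch.

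**Conclusion.** The point holds as a conservative approximation that misstates power on the plan's own inputs. For an unadjusted Cox test, power at the enrolled 1,500 is about 89% at VE 56.25% (stated 80%) and about 79% at VE 50% (69% by the formula). At the other Table 4 sizes it is about 87–90%. The unadjusted lowest detectable VE is about 50–51% at the Protocol's rate. With R² of 0.1–0.2 it is about 52–56%, so the printed 56.25% lies at or just beyond the cautious end of that range.

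This rests on the formula being the one inferred from the match, on proportional hazards with a constant rate, on dropouts contributing no follow-up time, and on the R² range, which is assumed. The likelihood-ratio test is 1–3 points lower than the score and Wald tests. The decision to enrol 1,500 is not undermined.

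**What to change.** Choose one control rate for both documents (the Protocol has 60 and the SAP 80 per 100,000 person-days). Recompute Protocol Table 4 and SAP Table 1 by simulation, or by a method that uses the expected events in each arm and is checked against simulation. Name the method.

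Report two lowest detectable values for 1,500 enrolled: unadjusted (about 50–51% at the Protocol's rate), and with a stated R² allowance for age, prior vaccination and week (about 52–56% for R² 0.1–0.2). Do not replace 56.25% with 50% as the headline.

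In the same edit, correct the expected case count in Protocol 6.1.1. The 85 cases labelled VE 50% belong to VE 56.25% (300 × 0.1008 + 1,200 × 0.0454 = 84.7). At VE 50% the count is 30.2 + 62.1 = 92.3, or 78.5 after attrition.

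The cost is a short simulation and revised table entries, with no change to design, enrolment or analysis.
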